Kitelock™, 4% tetrasodium EDTA catheter lock solution is the sole product of SterileCare Inc, a private medical devices and equipment company registered federally in Canada, and based in Markham, Ontario. Kitelock™ is licensed as a medical device, class 2 (license #96962, issue date 2016-05-10), by Health Canada.

RESEARCH DESIGN AND METHODS

The primary objective of this study is to evaluate patient acceptability of tetrasodium EDTA catheter lock solution in home parenteral nutrition patients.

The secondary aims are to evaluate: side effects, time for preparation and injection, cost and patient satisfaction.

This is a prospective, open-label, single-center study of the patient acceptability of using tetrasodium EDTA catheter lock solution in home parenteral nutrition patients. At study baseline, all patients will be on normal saline/heparin lock solution (which they receive normally as current standard of care) for at least 1 month before starting the study, as per inclusion criteria.

Patients will then start with one month (30 days) of their usual heparin and saline flush followed by one month (30 days) of tetrasodium EDTA solution with withdrawal (when possible), followed by one month (30 days) of tetrasodium EDTA solution. During the last week of each of the aforementioned three months, the patients will be asked to evaluate the lock and flush. Patients will be followed and treated according to usual care during the study, except for the catheter lock solution.

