If flushing Tetrasodium EDTA lock solution through the catheter, repeat above steps but omit 5 - 7.

Cost analysis (this is an estimate which may be modified after the trial):

Type	Solution	Dispensing fee	SAP application	Distribution	Supplies*	Education
Saline/heparin	\$2/use	0	N/A	0/contract	0/contract	0
Tetrasodium EDTA	\$3.50/use	0	N/A	0/contract	10ml syringe without needle	0.5h (\$40/hr)
Saline/taurolidine	\$20/10ml	\$11,99	2h (\$55/h) Per patient		3-5ml syringe with needle	0.5h (\$40/hr)

Measures:

1. Patient acceptability

See Form 2 below

2. Patient satisfaction

See Form 2 below

3. Time to prepare tetrasodium EDTA catheter lock solution

(1) From starting to prepare to infuse TPN to starting the TPN infusion (form 1)

(2) From disconnecting TPN tubing to completing catheter lock solution (form 1)

4. Symptoms and side effects

See Form 1: patient data collection form

5. Labs

Regular TPN labs, as per usual care, at the beginning and end of the study (form 4)

(1) Within 30 days of starting the study

(2) On, or up to 10 days after the last day of using the tetrasodium EDTA lock solution

Data collection forms:

-Form 1: patient data collection form:

-Record symptoms and side effects as they occur

-Record the time of the procedure on the first and last Monday of each 30-day period

-Form 2: survey on ease of use (3 per patient)

- to be filled by person administering the lock (RN, patient, family member), where possible

- to be filled three times, during the phone visit at the end of each month

- Form 3: Education time

-Nurse: over the phone

-Patient demonstration

Clinic Visits:

Clinic visits: None required

Follow up Phone call:

Each phone call will last for around 40 minutes. All participants will receive phone call at baseline and at the end of month 1,2 and 3.

Phone visits:

- (1) At baseline, prior to initiation of the product
- (2) At the end of month 1 (on days 27 to 30)
- (3) At the end of month 2 (on days 57 to 60)
- (4) At the end of month 3 (on days 87 to 90)

Follow-up phone call for the following purpose:

- **Safety:** by asking questions about side effects and tolerance to tetrasodium EDTA solution (from patient data collection form)
- **Compliance:** Recording the number of catheter lock solutions used.
- **Record times of procedure** (from patient data collection form)
- **Record events** (hospitalizations, antibiotics used, or interruption of lock solution use)

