- Congenital anomaly/ birth defect
- Important medical events that may not result in death, be life threatening, or require hospitalization may be considered an SAE when, based upon appropriate medical judgment, they may jeopardize the subject or may require medical or surgical intervention to prevent 1 of the other outcome listed in this definition.

Data storage:

All data regarding the study will be stored in hospital file and UHN computer system of the clinical fellow, nurse coordinator and principal investigator for 10 years.

Statistical analysis:

Simple statistics such as mean, median and frequency will be used to initially assess the data as follows:

1. Patient acceptability will be analyzed as the proportion of participants willing to continue use of the catheter lock solution. The solution will be deemed acceptable if at least 75% of participants are willing to continue use of the solution.

2. Patient satisfaction will be analyzed as the proportion of participants overall satisfied with the catheter lock solution.

3. Ease of use will be analyzed as the proportion of participants answering that the process is easy or very easy. This will be calculated by taking the average of the answers to the 3-5 questions at the top of the questionnaire addressing the ease of the procedure (preparation of the solution, instilling, withdrawing etc). Each step will also be analyzed individually (averaged over all of the patients), to determine if one of these individual averages falls below 3 (suggesting that that procedure is difficult).

The means of patient acceptability, patient satisfaction and ease of use of the new catheter lock solution flush and the new catheter lock solution withdraw will each be compared, separately, to those of the heparin group and to each other using the chi squared test to determine if there is any difference between them.

Sample Size and Feasibility

This is a pilot study; we plan to recruit 20 participants.

Limitations:

- The expected sample size is 20 subjects and some of them live far away from TGH. This can be avoided a phone call follow-up every month.
- Some of the patients may not be compliant with the catheter lock solution or TPN infusion. Compliance will be checked by counting the number of catheter lock solutions and tpn bags delivered and used. However, compliance cannot be predicted.

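### Acceptability, satisfaction and ease of use are compared between periods by a chi-squared test for independent groups although the same patients supply all three periods, and ease of use is called a proportion but calculated as an average with no rule joining the two

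*Protocol*

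**What the plan says.** **Outcome definition.** In the protocol's Statistical analysis section, item 3 begins: "Ease of use will be analyzed as the proportion of participants answering that the process is easy or very easy". The next sentence reads: "This will be calculated by taking the average of the answers to the 3-5 questions at the top of the questionnaire". The item's only numerical threshold is for single steps, each averaged over all patients, "to determine if one of these individual averages falls below 3 (suggesting that that procedure is difficult".

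**Comparison.** The paragraph after item 3 begins "The means of patient acceptability, patient satisfaction and ease of use of the new catheter lock solution flush", adds the withdraw procedure, and says that these "will each be compared, separately, to those of the heparin group and to each other using the chi squared test".

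**Design.** Under Research Design and Methods: "Patients will then start with one month (30 days) of their usual heparin and saline flush followed by one month (30 days" of EDTA with withdrawal and then a month of EDTA without it. Patients evaluate the lock in the last week of each month. Data collection forms lists Form 2 as "survey on ease of use (3 per patient", to be completed by whoever administers the lock: nurse, patient or family member.

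**The concern.** Two things do not fit together.

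**The test and the design.** An ordinary chi-squared test compares counts from independent groups. Here the heparin answers and both sets of EDTA answers come from the same 20 patients. The test ignores which patients changed and in which direction, and that is the information a within-patient design provides. The sentence covers all three outcomes, so the problem is not confined to ease of use.

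**The endpoint and its calculation.** An average of item answers is a score, not a proportion of participants. One could average each participant's answers and then count those whose average is 'easy', but that needs a participant-level rule, and item 3 gives none.

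At stake is the protocol's statement of whether EDTA differs from heparin. Ease of use is in the study title, and the Significance section gives it as a reason why EDTA might replace heparin. The study is open-label, so a rule for 'easy' chosen after the answers are known would be open to a favourable choice.

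**Working it through.** **Inputs.** From the protocol: 20 participants, three periods per patient, chi-squared test. Assumed, because the protocol gives no values: two-sided 5% level, chi-squared without continuity correction, all 20 patients rated in both periods compared, within-patient correlation of 0, 0.3 or 0.5. The protocol states no power or p-value to reproduce.

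**1. What ignoring the pairing does to the standard error.** With proportions p1 and p2, n patients and correlation r:

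- treated as independent: variance = [p1(1−p1) + p2(1−p2)]/n
- paired: the same, minus 2r·√[p1(1−p1)p2(1−p2)]/n

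For 75% v 75% and n = 20, the independent variance is 2 × 0.1875/20 = 0.01875 (SE 0.137). At r = 0.3 the paired variance is 0.01875 × 0.7 = 0.013125 (SE 0.115). At r = 0.5 it is 0.01875 × 0.5 = 0.009375 (SE 0.097). With positive correlation the chi-squared test therefore uses too large a standard error.

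**2. Rejection rate with no difference.** All paired tables for n = 20 were enumerated, with both periods at 75%:

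| Correlation | Chi-squared | Exact McNemar |
|---|---|---|
| 0 | 5.1% | 1.8% |
| 0.3 | 2.1% | 1.0% |
| 0.5 | 0.7% | 0.4% |

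**3. A consistent change that chi-squared misses.** Suppose 14/20 rate one period easy and 8/20 the other: 8 patients easy in both, 6 only in the first, 0 only in the second, 6 in neither.

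- Pooled proportion = 22/40 = 0.55. Chi-squared = 0.30² / (0.55 × 0.45 × 2/20) = 0.09/0.02475 = 3.64, p = 0.057 (0.112 with continuity correction).
- Exact McNemar, changes 6 v 0: p = 2 × (1/2)⁶ = 0.031.

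This table implies a correlation of (8 × 6 − 6 × 0)/√(14 × 6 × 8 × 12) = 0.53.

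**4. Power for a true difference, 80% v 50%,** by the same enumeration:

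| Correlation | Chi-squared | Exact McNemar |
|---|---|---|
| 0 | 53% | 37% |
| 0.3 | 53% | 48% |
| 0.5 | 52% | 58% |

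At 0.5 the chance of being easy only in the lower period is 0.50 − (0.80 × 0.50 + 0.5 × 0.20) = 0. So 0.5 is the highest correlation these two proportions allow.

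**5. Ease of use.** Form 2 is not in the text at hand, so assume a 1–5 scale with 4 = easy and 5 = very easy. A participant answering 4, 4, 4, 3 averages 15/4 = 3.75. That is above the 3 used to flag a difficult step but below the value for 'easy'. Item 3 does not say how this participant counts.

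**The case against.** **It is a small pilot with loose wording.** No significance level is stated, ease of use is not among the listed aims, and the mean of a yes/no answer is a proportion, so 'means' may be shorthand. That reading is fair for acceptability and satisfaction, which are defined as proportions. It does not cure the pairing, and it does not turn an average of several graded answers into a proportion.

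**A scoring cut-off is commonly left to the SAP.** True of a cut-off alone. Here the protocol itself states the endpoint, the calculation and the test, and they do not agree. The named category does make the scale value for 'easy' the natural cut-off, so this part is a clarification.

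**The replacement is not clearly better on error rates.** This stands in part. Exact McNemar is more conservative than chi-squared with no difference at every correlation tried, and has less power at correlations 0 and 0.3. The case rests on matching the test to the design and showing who changed, not on a general gain in power.

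**Stronger readings that a reader might infer.** One is that the chi-squared test produces false positives. The enumeration does not show this: rejection stays near 5% at zero correlation and falls below it as correlation rises. Tables where chi-squared is significant and McNemar is not can be built, but the widest gaps need a negative correlation, which is unlikely for repeated ratings from one patient. Another is that averaging each step and flagging values below 3 is an error. It is a coherent screening flag, and the section also plans medians and frequencies.

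**Conclusion.** The concern holds in two parts.

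First, the named test does not fit the design for any of the three outcomes. With positive within-patient correlation it is conservative (2.1% and 0.7% at correlations 0.3 and 0.5, against 5%) and can miss a consistent change (p = 0.057 v 0.031 in the example). These figures assume 20 complete pairs, a 5% level and no continuity correction. The correlation is unknown.

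Second, the stated calculation for ease of use does not yield the stated endpoint. How much this matters cannot be sized without Form 2.

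A reader might infer that the primary conclusion is at risk. The documents do not support that: the rule that at least 75% must be willing to continue uses neither this test nor the ease-of-use score. Only the comparisons between periods are affected, including the one for acceptability. The change should be made, but it is of moderate weight.

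**What to change.** In the Statistical analysis section:

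1. Replace the chi-squared test with within-patient comparisons for all three outcomes. Use exact McNemar for proportions, reporting the numbers changing in each direction. If ease of use is kept as an average score, use a paired signed-rank test. Refer to the heparin period, not a heparin group.
2. Before data are seen, state the scale and one participant-level rule for 'easy' in each period. An example is a mean over the steps that apply to that procedure at or above the scale value for 'easy'.
3. Identify pairs in which different people completed the two surveys. The follow-up calls already record who does the flush.

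**Cost.** Wording and a little extra analysis on survey answers already planned. The real downside is power when correlation is low: for 80% v 50%, exact McNemar has 37% against 53% at correlation 0 and 48% against 53% at 0.3, and gains only at 0.5 (58% against 52%). It also cannot reach p < 0.05 with fewer than six changes, all in one direction (5 v 0 gives 2 × (1/2)⁵ = 0.0625).

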APPENDIX

Sample size: 20 participants

Duration: 3 months

Patient will be instructed on the use of the new lock solution via:

A Telephone by HPN nurse OR

B Demonstration by company representative

Patient will receive four phone calls from HPN nurse in regards to this study:

1st- beginning of the study

2nd- end of first month

3rd- end of second month

4th- end of third month

After first phone call, the subsequent phone call is to record:

1. Time to perform the task

2. Symptom or side effects that patient has written down in their data collection

3. Survey
